1. REPORTING & ANALYSIS PLAN SYNOPSIS

Overview	Key Elements of the RAP
Purpose	The purpose of this reporting and analysis plan (RAP) is to describe all planned analyses and output requirements during the study.
Protocol	This RAP is based on the original protocol / protocol amendment 2[(Dated: 21/09/2015) of study MID201283(GSK Document No.: 2014N211002_02] and eCRF Version 3.
Primary Objective	There is no primary objective/endpoints in this protocol. See Section 2.2 for exploratory objectives/endpoints.
Primary Endpoint	There is no primary objective/endpoints in this protocol. See Section 2.2 for exploratory objectives/endpoints.
Study Design	
An exploratory, non-controlled, non-drug study in ALS patients. The study consists of two phases:
 
 1. A variable length Pilot Phase to test and confirm the algorithms are capturing movement/physical activity, ensure the data transfer device is working correctly, and understand the reliability and ease of use/acceptance of the accelerometer and electrode. 2. A 48-week Core Study Phase to evaluate how measures of movement/physical activity, speech and HRV relate to ALS disease progression.
Planned Analyses	
A hierarchical approach will be used to focus the analysis on the endpoints where a correlation with either the ALSFRS-R or FVC (as applicable) is present. To begin with, the correlation between the following endpoints will be explored using the analysis method detailed below:
 
 • The absolute and change from baseline in the movement/physical activity endpoints as measured by the accelerometer device and the change from baseline in the ALSFRS-R • The absolute and change from baseline in the heart rate variability endpoints as measured by the electrode device and the absolute and change from baseline in the ALSFRS-R • The absolute and change from baseline in the speech endpoints and the absolute and change from baseline in the ALSFRS-R • The absolute and change from baseline in the speech endpoints and the absolute and change from baseline in the FVC 
If there's correlation between these endpoints, then further analyses as described in Section 9.7 will be carried out as part of adhoc.

Analysis Populations	
 • Enrolled population: This will consist of all subjects who have signed consent and are not a screen failure. • Full Analysis Set (FAS): This will consist of all subjects with at least one post baseline measure for the ALSFRS-R and at least one physical

Overview	Key Elements of the RAP
	
activity/movement measure, night time rest, Heart Rate Variability or Speech assessment endpoint.
 
 • Safety: Comprise of all subjects who carried out at least one protocol specified procedure. • Screen Failure: Comprise of all subjects who were a screen failure
Hypothesis	
 • The study is designed to explore if there is a relationship between change from baseline in the physical activity/movement, night time rest, heart rate variability and speech endpoints and change from baseline in the gold standard measures of function (ALSFRS-R and FVC).

2. SUMMARY OF KEY PROTOCOL INFORMATION

2.1. Changes to the Protocol Defined Statistical Analysis Plan

[figure not shown]
There were no changes or deviations to the originally planned statistical analysis specified in the protocol.

2.2. Study Objective(s) and Endpoint(s)

Objectives	Endpoints
Exploratory Objectives	Exploratory Endpoints

Explore the application of actigraphy:
 
 • For measuring movement/physical activity in ALS subjects • As a marker of ALS disease progression 	
 • Change over time in measurements of movement/physical activity by accelerometer-reported by day and night time. Measurements include Duration of wear time, (combining day & night values to give Wear time), Overall time spent active, Overall time spent sedentary not lying, Overall time spent lying, Overall time spent sedentary, Time spent with Sensor off, Total Activity Score, the maximum score from a 1 min window in a 24-hour period and 5 x Active Periods (5 categories: >1 to <=2min active up to >30mins active) • Change over time in measurements of night time rest by accelerometer reported endpoints: Percent Time Lying Down (at night), Number Night Time Movement Episodes, Number Night Time Movement Episodes/Hr, Percent Time Night-time Rest Efficiency, Rest Fragmentation Index =Move Time/Num Movement Episode, Average Duration Movement Episodes • Relationship between the ALSFRS and accelerometer measures of movement/activity and night time rest endpoints.

Explore the application of continuous remote monitoring of heart rate measures:
 
 • For measuring autonomic nervous system function in ALS subjects • As a marker of ALS disease progression 	
 • Change over time in heart rate variability (HRV) as measured by a heartbeat sensing electrode. Measurements include: 
 ○ Mean and variance for LF/HF (lying, sedentary not lying, active). ○ Mean and variance for HRV effect of being upright = LF/HF sedentary not lying minus LF/HF lying ○ Mean and variance for HRV effect of activity = LF/HF active minus LF/HF lying ○ Mean and variance for RMSSD (24 hours)

Objectives	Endpoints
	
 • Relationship between the ALSFRS and biotelemetry measures of HRV.

Explore the application of digital, quantitative speech testing:
 
 • For measuring speech quality in ALS subjects • As a marker of ALS disease progression. 	
 • Change over time in digital speech measures of vowel, running speech and word measurements as captured by a high fidelity, acoustic sound capture interface. Measurements include: central tendency of fundamental frequency, jitter, shimmer, maximum gap between words, speaking rate, average phoneme rate, maximum phonation time and % pause time • Relationship between the ALSFRS and digital measures of speech. • Relationship between Forced Vital Capacity (FVC) and digital measures of speech.

Explore the impact of the accelerometer and electrode devices on everyday life in subjects with ALS
	
Subject/caregiver feedback. Feedback may include but not be limited to: comfort of the devices, ease of applying the devices, and ease of data transmission process.

Explore the feasibility of biotelemetry transmission of movement/physical activity and HRV data.
	
Assessed by successful data transmission from the telecommunications hub (Life Insight) to the central secure server at McLaren Applied Technologies (MAT).

Safety Objectives
	
Safety Endpoints

Monitor safety and tolerability.
	
 • Type and incidence of adverse events (AEs) secondary to the devices used in this study. • Type and incidence of AEs due to study procedures.

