9.2. Appendix 2: Study States and Phases

9.2.1. Treatment States for AE Data

Treatment State	Definition
Onset Time Since 1 st (Days)	If Start Date of wearing the device or date of first protocol specified procedure > AE Onset Date Onset Date = AE Onset Date - Start Date of wearing the device If Start Date of wearing the device or date of first protocol specified procedure ≤ AE Onset Date Onset Date = AE Onset Date - Start Date of wearing the device + 1 Missing otherwise.
Duration (Days)	AE Resolution Date – AE Onset Date + 1
Study-related	If relationship to study participation marked 'YES' on [Inform/CRF OR value is missing].

Note: wearing the device refers to either the at home monitoring, or the use of the device to carry out the in clinic set reference tasks.

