9.4.2. Study Population

Demographics
Age

 GSK standard IDSL algorithms will be used for calculating age where birth date will be imputed as follows: 
 Any subject with a missing day will have this imputed as day '15'. Any subject with a missing date and month will have this imputed as '30th June'. Birth date will be presented in listings as 'YYYY'.

Adverse Event
For this non-drug study, an AE is any untoward medical occurrence in a clinical investigation subject which, in the opinion of the investigator, is related to a protocol-mandated procedure or one of the devices used by the subject during the study.

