9.11.6. Safety Tables

Safety: Tables					
No.	Population	IDSL / TST ID / Example Shell	Title	Programming Notes	Deliverable [Priority]
Adverse Events					
3.1.	Safety	AE1CP	Summary of All Adverse Events	Add a Footnote: Only those AEs and SAEs which, in the opinion of the investigator, are related to a protocol-mandated procedure or one of the devices used in the study will be reported	SAC
3.2.	Safety	AE1CP	Summary of Serious Adverse Events		SAC
3.3.	Safety	AE1CP	Summary of Adverse Events Leading to Withdrawal from Study		SAC
3.4.	Safety	AE5A	Summary of Adverse Events by Maximum Intensity		SAC
3.5.	Safety	SAFE_T1	Summary of Deaths		SAC

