9.11.7. ICH Listings

ICH : Listings					
No.	Population	IDSL / TST ID / Example Shell	Title	Programming Notes	Deliverable [Priority]
Subject Disposition					
1.	Screen Failure	ES7	Listing of Reasons for Screen Failure		SAC
2.	FAS	ES2	Listing of Reasons for Study Withdrawal		SAC
Protocol Deviations					
3.	FAS	DV2	Listing of Important Protocol Deviations		SAC
4.	FAS	IE3	Listing of Subjects with Inclusion/Exclusion Criteria Deviations		SAC
Populations Analysed					
5.	Enrolled	SA3a	Listing of Subjects Excluded from Any Population		SAC
Demographic and Baseline Characteristics					
6.	FAS	DM2	Listing of Demographic Characteristics		SAC
7.	FAS	DM10	Listing of Race		SAC
Prior and Concomitant Medications					
8.	FAS	MH3	Listing of Medical Conditions		SAC
9.	FAS	CP_CM3	Listing of Concomitant Medications		SAC
Adverse Events					
10.	Safety	CP_AE8	Listing of All Adverse Events		SAC
11.	Safety	CP_AE8	Listing of Drug Related Adverse Events		SAC
12.	Safety	CP_AE8	Listing of Serious Adverse Events		SAC
13.	Safety	CP_AE8	Listing of Adverse Events Leading to Withdrawal from Study		SAC

ICH : Listings					
No.	Population	IDSL / TST ID / Example Shell	Title	Programming Notes	Deliverable [Priority]
14.	Safety	CP_AE8	Listing of Adverse Events by Maximum Intensity		SAC
Death					
15.	Safety	SAFE_L1	Listing of Deaths		SAC

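### Device-related and procedure-related AEs are declared as two safety endpoints, but the AE tables give only their union and no specified variable separates them

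*SAP*

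**What the plan says.** Under the objective of monitoring safety and tolerability, SAP Section 2.2 lists two endpoints as separate bullets: "Type and incidence of adverse events (AEs) secondary to the devices used in this study" and "Type and incidence of AEs due to study procedures".

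Section 9.4.2 defines an AE for this study as an untoward occurrence that, in the investigator's opinion, "is related to a protocol-mandated procedure or one of the devices used by the subject during the study". The programming note for Table 3.1 in Section 9.11.6 asks for a footnote to the same effect: only events that "are related to a protocol-mandated procedure or one of the devices used in the study will be reported".

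Section 9.2.1 derives one relatedness item, 'Study-related'. Its rule reads "If relationship to study participation marked 'YES' on [Inform/CRF OR value is missing", so a missing answer counts as related.

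Table 4 (Section 7.2.1) plans summaries of all AEs and serious AEs by SOC, AEs leading to withdrawal by SOC and preferred term, AEs by intensity, and deaths. Section 9.11.6 turns these into Tables 3.1 to 3.5, starting with "Summary of All Adverse Events". In Section 9.11.7, Listing 11 is the "Listing of Drug Related Adverse Events". Section 1 describes the study as non-drug, and Section 2.3 gives dosing as not applicable.

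**The concern.** Each endpoint asks for its own type and incidence, so each needs its own numerator. The display list supplies one numerator for the two together, and the derivations contain nothing from which a programmer could form the others.

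The distinction matters here. The accelerometer and electrode are worn at home for about three days at a time up to Week 48. The reference tasks, FVC and speech assessment take place in clinic. Someone deciding whether to use the devices in a later ALS study wants the incidence of events caused by wearing them, without events caused by the clinic procedures. The plan names that quantity as an endpoint and then schedules no output that shows it.

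**Working it through.** No sample size, power or event figure bears on this point, so the check traces the two endpoints through the SAP.

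1. **AE definition (9.4.2) and Table 3.1 footnote (9.11.6).** Both join the causes with 'or'. The set of reported AEs is the union of the two endpoints, with no rule for telling them apart.

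2. **Relatedness flag (9.2.1).** The flag is yes if the event is marked as related to study participation, and also yes if that field is blank. An event enters the AE set only if the investigator already judged it related to a procedure or a device. A record marked no would sit awkwardly with that definition. The flag should therefore be yes for essentially every AE. This follows from the definitions and is not an observed figure.

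3. **Summary tables (7.2.1, 9.11.6).**

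| Table | Content | Split by device or procedure |
|---|---|---|
| 3.1 | All AEs | No |
| 3.2 | Serious AEs | No |
| 3.3 | AEs leading to withdrawal | No |
| 3.4 | AEs by maximum intensity | No |
| 3.5 | Deaths | Not an AE table |

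The count is 0 of 4 AE tables.

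4. **Listings (9.11.7, 9.11.8).** Listings 10 to 16 are the seven safety listings. Listing 15 is deaths, which leaves six for AEs. One of the six, Listing 11, carries a cause in its title, and that cause is a drug. No drug is given, so read literally it has no referent. Read as 'Study-related' it would, by step 2, essentially repeat Listing 10. It has no matching row in Table 4.

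5. **What the pooled count allows.** Let X be the number of subjects with any AE, D the number with a device AE, P the number with a procedure AE and B the number with both. Then X = D + P − B. The tables give X only. D and P can each be anything from 0 to X, provided D + P ≥ X. That holds for any unsplit count, so it shows that the split cannot be recovered from the tables and says nothing about how large the difference would be in this study.

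**The case against.** A reader might infer that neither endpoint is reported at all. The SAP does not support that. By its own definition every AE belongs to at least one of the two endpoints, so Tables 3.1 to 3.4 do give the type and incidence of the union, and Listing 10 shows each event. Events as unlike as a fall and a skin reaction would normally appear in different SOC rows, so type is partly readable. Nor is it right to say that every safety table pools the causes, since Table 3.5 counts deaths.

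The shell for the AE listings (CP_AE8) and the eCRF page are not shown. A cause column in Listing 10 cannot be ruled out, and Section 9.2.1 lists derived items, not every collected field. It would be wrong to conclude that attribution is not collected.

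The causes also overlap. Sensor placement is itself a scheduled procedure, and the device is worn during the clinic reference tasks. Section 9.7.1 calls the number of subjects small, and with few events a line listing may show cause well enough. Device acceptability is also covered by the diary and device-impact summaries (Tables 2.146 and 2.147).

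These points narrow the concern without removing it. A listing column is not an incidence, and Section 2.2 asks for incidence. SOC is not an attribution, and the SAP gives no rule for inferring cause from it. The diary and questionnaire measure acceptability, not AEs. The overlap is a reason to define a 'both' category. The mislabelling of Listing 11 stands whatever view is taken of the pooling.

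**Conclusion.** The concern holds in this form: followed as written, the plan yields no separate incidence for device-related or procedure-related AEs, although Section 2.2 declares both. None of the four AE tables separates them, the single relatedness flag cannot do so, and Listing 11 is titled for a cause that does not exist in this study. This is a mismatch inside the SAP, between its own endpoint list and its own display list, and not a matter left to the protocol.

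The size is a reporting gap: information is lost in the summaries, and no estimate is shown to be biased. How far device incidence differs from the pooled figure cannot be judged from the document. The conclusion assumes that the unseen table shell AE1CP adds no split by cause, which no table title, programming note or derivation suggests. It does not depend on whether the eCRF records cause.

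**What to change.** - **Attribution variable.** In Section 9.2.1, next to 'Study-related', define attribution as device, procedure or both, taken from the investigator's causality judgement that Section 9.4.2 already requires. If the eCRF does not separate the two, query the site before database freeze. The sponsor should not assign cause from the verbatim term, since that would replace the investigator's opinion with inference.
- **Missing values.** State a rule. One option is to keep events with no attribution after query in the pooled count and show them in a row of their own.
- **Summaries.** Add device-related and procedure-related incidence by SOC and preferred term, at least to Table 3.1. Count events with both causes in both blocks, and footnote that the blocks need not sum to the total.
- **Listings.** Add an attribution column to the AE listings, and replace Listing 11 with a listing of device-related AEs. Update Table 4 to match.

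If the sponsor means to combine the two endpoints, Section 2.2 should say so; Listing 11 would still need correcting.

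The cost is RAP wording, one derived variable, one extra block or table, and possibly one query per AE.

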2.3. Study Design

Overview of Study Design and Key Features	
	reference tasks while wearing the accelerometer and electrode. Subjects will also continuously wear the accelerometer and electrode in their routine home-life setting for approximately 3 days after the clinic visits (i.e., home monitoring). In between clinic visits, subjects will attach the accelerometer and electrode and wear it for approximately 3 days in their home. A telephone contact with the subject will be made by the site at the end of each 3-day home monitoring period.
Dosing	
 • NA
Treatment Assignment	
 • This study doesn't include any treatment • Treatment of enrolled subjects will be consistent with local standard of clinical care for ALS patients
Interim Analysis	
 • No formal interim analyses will be performed

2.4. Statistical Hypotheses

The study is designed to explore if there is a relationship between change from baseline in the physical activity/movement, heart rate and speech endpoints and change from baseline in the gold standard measures of function (ALSFRS-R and FVC).

3. PLANNED ANALYSES

3.1. Interim Analyses

No formal interim analyses will be performed. Review of in stream data will be carried out to understand the utility of the measures and algorithms, the functionality of the data transmission process, and the durability and ease of use/acceptance of the selected accelerometer and electrode. Generated data may result in modifications to the study, such as: changes to the devices/equipment; repositioning of the accelerometer/electrode; modification to the algorithms, the supportive data collection plan or the data transmission process; dropping measures/tests which are not achievable.

McLaren Applied Technologies will not have access to the ALSFRS-R or FVC data and so modifications to the algorithms will be based solely on data collected from the accelerometer/ speech device. All modifications to the algorithms will be documented and version controlled.

3.2. Final Analyses

The final planned exploratory analyses will be performed after the completion of the following sequential steps:

1. All subjects have completed the study as defined in the protocol
2. All required database cleaning activities have been completed and final database release and database freeze has been declared by Data Management.

4. ANALYSIS POPULATIONS

Population	Definition / Criteria	Analyses Evaluated
Enrolled	
 Comprise of all subjects who have signed consent and are not a screen failure 	
 Study population
Full Analysis Set (FAS)	
 This will consist of all subjects with at least one post baseline measure for the ALSFRS-R and at least one physical activity/movement measure. 	
 Study Population Exploratory
Safety	
 Comprise of all subjects who carried out at least one protocol specified procedure. 	
 Safety
Screen Failure	
 Comprise of all subjects who were a screen failure 	
 Study Population

NOTES:

- Please refer to [Appendix 11](#): List of Data Displays which details the population to be used for each displays being generated.

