7. STATISTICAL ANALYSES

7.1. Exploratory Analyses

7.1.1. Overview of Planned Exploratory Analyses

The efficacy analyses will be based on the “Full Analysis Set” population, unless otherwise specified.

Data Quality Deviators (for data points at each protocol time point):

Activity & Night time Rest endpoints

For all the actigraphy endpoints if the difference between visits of ALSFRS and Actigraphy is more than 21 days then the data will be excluded and will not be used for the summaries. If the first time point within a visit falls within the 21 days window, then all the time points will be considered.

Using the default sleep times for this study (22:00-07:00) which are derived from the day and night anchor times (set by the day/night algorithms used in this study), the amount of data present for a 24-hour recording period was calculated by adding up the durations for activity classifiers: active + sedentary [where sedentary = sedentary not lying + lying]. If the amount of data present is too low (conversely the amount of “off” time is too high) then the data will not be representative of a full day or night, because a subject’s pattern of activity throughout a day or night is not expected to be homogenous or uniform.

A review of the literature showed that a variety of rules can be used, ex. for daytime recordings: 70-75% of data present, 10 of 16 hours (63%) data present. There are not set rules or standards. As this study utilises 22 hours recording (2 hours permitted for charging), the study team decided on the following limits: 70% for the day and 60% for the night. The % is set lower for the night as it was recognised that subjects may have more problems with night (either due to their disease, or with the technology) and so the amount of valid usable data for a night might be expected to be less. [Tudor-Locke, 2012]

Daytime Endpoints

Any data point associated with a 24-hour recording period (1440 minutes), or for a partial recording period, for DAY TIME with <9.1 hours of data for the day time is considered as a data quality data point deviator.

Day = 15 hours, permit 2 hours charging = 13 hours. 70% of 13 hours = 9.1 hours. Exclude data point if active day+sedentary day = <9.1 hours

Night time Endpoints

Any data point for a 24-hour recording period (1440 minutes), or for a partial recording period, for NIGHT TIME with <4.2 hours of data for the night time is considered as a data quality data point deviator.

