9.1. Appendix 1: Time & Events

9.1.1. Protocol Defined Time & Events

Table 1 Time and Events – Pilot Phase

Procedures	Clinic Visit	Home Monitoring (~ 3 days)	Telephone Contact ^a (TC)	Repeat Clinic Visit ^b	Home Monitoring ^b (~ 3 days)	Telephone Contact ^{a,b}	EWD
	Screening Day 0						
Informed consent	X						
Eligibility criteria	X						
Demography	X						
Medical and ALS history	X						
Brief neurological exam	X			X			
AEs/SAEs	X		X	X		X	X
Sensor placement	X	X		X	X		
Reference tasks	X			X			
Subject completes diary		X			X		
Site obtains diary information			X			X	X
Device impact questionnaire			X			X	X

- a. Telephone contact to follow the 3-day home monitoring period to ensure the subject has completed the home monitoring period, diary, and to assess AEs, as appropriate. The expectation is that this call would occur on the first weekday following the home monitoring period.
- b. May be repeated as necessary

Table 2 Time and Events – Core Study Phase

Study Day/Week ^a	Screen/Baseline Day 1/Week 0	Weeks 0, 4, 8	Week 12	Weeks 12, 16, 20	Week 24	Weeks 24, 28, 32	Week 36	Weeks 36, 40, 44, 48 ^c	Week 48 or EWD
	Clinic Visit 1 ^b	Home Monitoring (~3 days)	Clinic Visit 2	Home Monitoring (~3 days)	Clinic Visit 3	Home Monitoring (~3 days)	Clinic Visit 4	Home Monitoring (~3 days)	Clinic Visit 5
Procedures									
Informed consent	X ^d								
Eligibility criteria	X ^d								
Demography	X ^d								
Medical and ALS history	X ^d								
Neurological exam	X								
Smoking details	X		X		X		X		X
Brief neurological exam			X		X		X		X
AEs/SAEs ^e	X	X	X	X	X	X	X	X	X
Concomitant medications ^e	X	X	X	X	X	X	X	X	X
ALSFRS-R ^e	X	X	X	X	X	X	X	X	X
FVC	X		X		X		X		X
Speech assessment	X		X		X		X		X
Sensor placement	X	X	X	X	X	X	X	X	X
Reference tasks	X		X		X		X		X
Device impact questionnaire			X		X		X		X
Subject completes diary		X		X		X		X	
Site obtains diary information ^f		X	X	X	X	X	X	X	X
Follow-up Telephone Contact ^g		X		X		X		X	

- a. Clinic visits and home monitoring periods should be conducted within ± 7 days of the scheduled visit/home period and should be scheduled according to the Baseline Visit.
- b. Subjects transitioning from the Pilot Phase do not need to perform these procedures.
- c. The Week 48 home monitoring period will occur the three days prior to the Week 48 in-clinic visit (Visit 5).
- d. Assessed in clinic at Weeks 0, 12, 24, 36, and 48 and by telephone at Weeks 0, 4, 8, 12, 16, 20, 24, 28, 32, 36, 40, and 44.

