- e. Assessed in clinic at Weeks 0, 12, 24, 36, and 48 and by telephone at Weeks 4, 8, 16, 20, 28, 32, 40, and 44.
- f. Diary information should be obtained by telephone at Weeks 0, 4, 8, 12, 16, 20, 24, 28, 32, 36, 40, and 44.
- g. Telephone contact to follow each 3-day home monitoring period. The expectation is that this call would occur on the first weekday following the home monitoring period.

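### Wear-time, diary, device-impact, disposition, deviation and withdrawal-reason displays sit on the FAS, which requires a post-baseline ALSFRS-R that the Pilot Phase never collects

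*SAP*

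**What the plan says.** Section 4 defines the FAS: "This will consist of all subjects with at least one post baseline measure for the ALSFRS-R and at least one physical activity/movement measure". The synopsis also lets a subject qualify on the device side through "activity/movement measure, night time rest, Heart Rate Variability or Speech assessment endpoint", but it keeps the same ALSFRS-R condition. Section 4 leaves the population of each display to Appendix 11.

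Appendix 11 assigns the FAS to:
- wear time: Tables 2.1–2.6, each to be split into Pilot and Core pages, and Listings 17–22;
- diary and device impact: Tables 2.146–2.147 and Listings 66–67;
- disposition: Table 1.1;
- protocol and eligibility deviations: Table 1.4 and Listings 3–4;
- reasons for withdrawal: Listing 2.

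The synopsis gives the Pilot Phase, among other purposes, the task to "understand the reliability and ease of use/acceptance of the accelerometer and electrode". Section 2.2 has a separate objective: "Explore the impact of the accelerometer and electrode devices on everyday life in subjects with ALS".

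**The concern.** The Pilot Phase is there partly to learn whether patients can and will use the devices. A subject who tries them in the Pilot and goes no further has direct evidence on that question. Under the plan, that subject's wear time, diary answers and device-impact answers are left out because a disease scale was not recorded, and the Pilot never schedules that scale.

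Disposition and withdrawal reasons have a related problem. Their purpose is to account for everyone who entered, but they are reported on a set that can exclude early leavers. What is at stake is the completeness of the feasibility and participant-flow reporting. The correlation results are not affected.

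**Working it through.** The SAP states no figure for this point, so the check compares the definitions, the two schedules in Section 9.1.1 and the population column of Appendix 11.

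**1. Pilot.** The schedule headed "Table 1 Time and Events – Pilot Phase" has 11 procedure rows. None is ALSFRS-R. It does include sensor placement, the diary and the device impact questionnaire, and the last two are also collected in its early-withdrawal column. A subject seen only in the Pilot therefore has usable feasibility data but cannot meet either FAS definition. The Pilot pages of Tables 2.1–2.6 can hold only subjects who moved to Core and had a post-baseline ALSFRS-R there.

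**2. Core.** ALSFRS-R is done at the clinic visits "and by telephone at Weeks 4, 8, 16, 20, 28, 32, 40, and 44". It is also marked in the Week 48/early-withdrawal column. The Week 0 telephone contact may serve as baseline (Section 9.3.2.1), so the first scheduled post-baseline value is at Week 4. To fall outside the FAS on this condition, a subject must leave with no Week 4 value, no later value and no early-withdrawal assessment. That is possible but narrow. Core device impact is collected only in columns that also carry ALSFRS-R, so for Table 2.147 the loss is essentially the pilot-only subjects.

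**3. Share missing.** Let E be the number enrolled, P the pilot-only subjects and C the Core subjects with no post-baseline ALSFRS-R. At least (P + C)/E of enrolled subjects are absent from the named displays. The SAP gives none of the three, so the share cannot be calculated.

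**4. Effect on Table 1.1, Core part.** Let N be the Core subjects, W the withdrawals and k the withdrawals with no post-baseline ALSFRS-R. Section 9.5.1 defines a completer as someone followed through Week 48, when ALSFRS-R is due, so only withdrawals are taken to drop out on this condition.

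- True proportion: W/N.
- Displayed proportion: (W − k)/(N − k).

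With assumed N = 20 and W = 5:

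| k | Displayed | Result |
|---|---|---|
| 0 | 5/20 | 25.0% |
| 1 | 4/19 | 21.1% |
| 2 | 3/18 | 16.7% |

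Listing 2 lacks the same k subjects.

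**5. The 21-day rule.** Section 7.1.1 says of actigraphy that "if the difference between visits of ALSFRS and Actigraphy is more than 21 days then the data will be excluded". The Pilot has no ALSFRS-R visit of its own from which to measure 21 days. The quality-data wear-time tables (2.2, 2.4, 2.6) therefore have no workable rule for Pilot recordings, even for pilot subjects who do reach the FAS.

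**The case against.** The strongest reply is that nothing may be lost. A footnote to the Core schedule foresees movement between phases: "Subjects transitioning from the Pilot Phase do not need to perform these procedures". If every pilot subject moved on and had a post-baseline ALSFRS-R, all of them satisfy the ALSFRS-R condition. The Core route out of the FAS is narrow, the study is exploratory, and the in-stream review in Section 3.1 also looks at device acceptance. All of this stands. It limits the likely size but does not make the FAS the right population for these displays.

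Three stronger readings are tempting, and the SAP does not support them.

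- A reader might infer that pilot-only subjects disappear from the report altogether. They do not. Their adverse events, AE-related withdrawals and deaths are shown on the Safety population (Tables 3.1–3.5, Listings 10–15). Table 1.5 and Listing 5, on the Enrolled population, disclose their exclusion. Because Listing 5 does this, it matters little that Listing 4, on the FAS, cannot show population exclusions.
- A reader might see a flat contradiction with Section 9.5.1, which promises to list all available data from withdrawn subjects. That sentence ends with an exception for cases specified otherwise, and Appendix 11 can be read as such a specification. The fit is poor, but it is not a clear conflict.
- A reader might argue that withdrawal could equally be overstated. That would require completers to be missing from the FAS, which in Core could come from the actigraphy clause in Section 4. The ALSFRS-R condition discussed here does not produce it.

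**Conclusion.** The point holds as a matter of definition. On the SAP's own text, pilot-only subjects cannot appear in the named displays, and neither can Core subjects without a post-baseline ALSFRS-R. The Pilot pages of the wear-time tables are the clearest case, because the plan asks for them and then restricts who can be on them.

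The practical size is unknown and may be zero. The 21.1% and 16.7% figures rest on an assumed 20 Core subjects and 5 withdrawals, and show only how the ALSFRS-R condition would act on Table 1.1. Neither the size nor the direction of any shift in wear-time or device-impact results can be derived from the SAP.

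This should be fixed, because the correction is cheap and concerns stated objectives of the study. It does not threaten the main analyses.

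**What to change.** In Appendix 11:

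- Set Tables 1.1, 1.4, 2.1–2.6 and 2.146–2.147, and Listings 2–4, 17–22 and 66–67, to the Enrolled population. Show Pilot and Core separately, each with its own denominator.
- Move the companion study-population displays (Tables 1.3 and 1.6–1.8; Listings 6–9) with them so that the Ns agree.
- Keep the FAS for the correlation analyses and for Table 2.143, which documents the data removed from them.
- Report Pilot wear time from the all-data tables. Footnote that the 21-day rule cannot be applied to Pilot recordings, and leave the definition of quality data unchanged.
- Take the meaning of Pilot completion from the protocol. Section 9.5.1 defines completion only through Week 48, which would make every pilot-only subject a non-completer.

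Separately, reconcile the synopsis and Section 4 definitions of the FAS into one wording.

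The cost is edits to the population column for 29 displays (10 tables and 11 listings named first, plus 4 tables and 4 listings as companions), phase-specific denominators, one footnote and one reconciled definition. No new data are needed. The downside is that the N of these displays will differ from that of the correlation tables, and the feasibility figures may look less favourable.
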